1.3. Sample Size Consideration

The initial sample size was calculated to support the primary objective of the study, that is, to evaluate trilaciclib's effect on PFS when administered prior to sacituzumab govitecan-hziy in patients with locally advanced or metastatic TNBC who received at least 2 prior treatments with at least 1 in the metastatic setting.

This single-arm study was initially planned to enroll 45 patients during the 10-month accrual period with an approximate 30-month total study duration. With 45 patients and 14 months of follow-up after the last patient is dosed, Table 2 presents the required number of PFS events and statistical powers to detect hazard ratios (HRs) of 0.7 and 0. 8 at a 2-sided significance of 0.2 for a median PFS of the historical control group of 5.6 months, which was defined for patients without brain metastases treated with sacituzumab govitecan-hziy in the Phase 3 ASCENT trial (Bardia, 2021). The calculation is based on a one-sample log-rank test (Wu, 2015) with the

assumption that the survival time distributions for both study treatment and historic control group follow the Weibull distribution with a shape parameter of 1.00 (i.e., exponential distribution). PASS 2019, v19.0.8 was used for the power and sample size calculation.

Table 2Statistical Power

Hazard Ratio	Median PFS for trilaciclib + sacituzumab govitecan-hziy (Months)	Expected number of events in the study	Statistical Power
0.70	8.0	36	80%
0.80	7.0	38	54%

On February 14, 2023, the sponsor decided to close enrollment to this study in order to reallocate resources to other ongoing trilaciclib clinical trials. The final sample size is 30.

G1 Therapeutics

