# 12.3. Timing of Planned Analysis

# 12.3.1. First Planned Analysis – Analyses for Progression-Free Survival, Tumor Response Endpoints, and Myelosuppression Endpoints

The first planned analysis will be conducted for the primary endpoint, PFS, at the time when 36 patients have radiographically-determined disease progression or have died. Study database will be locked to support the analysis. In addition, the following specified analyses will be performed:

- Analysis of tumor response endpoints (ORR, CBR, and DOR).
- Analysis of myelosuppression endpoints.
- Analysis of safety data.

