2. THE NUMBER OF PLANNED ANALYSES

2.1. Final Planned Analysis - Analyses for Progression Free Survival, Tumor Response Endpoints, Myelosuppression Endpoints, and Overall Survival

The final planned analysis will be conducted when approximately 70% of patients have died (i.e., 21 deaths). Study database will be locked to support the final OS analysis. The following specified analyses will be performed:

- Analysis of progression free survival.
- Analysis of tumor response endpoints (ORR, CBR, and DOR).
- Analysis of myelosuppression endpoints.
- Analysis of overall survival.
- Analysis of safety data.

The final planned analysis will be used to support the abbreviated clinical study report (aCSR).

G1 Therapeutics

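### Does SAP Table 2, with power for 45 patients, need replacing now that the final sample size is 30?

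*SAP*

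**What the plan says.** SAP Section 1.3 presents the power calculation as that of the initial design: "This single-arm study was initially planned to enroll 45 patients during the 10-month accrual period". It introduces the table with "With 45 patients and 14 months of follow-up after the last patient is dosed, Table 2 presents the required number of PFS events". The calculation is a one-sample log-rank test under exponential survival, "at a 2-sided significance of 0.2", "for a median PFS of the historical control group of 5.6 months". Table 2 gives 36 events and 80% power at a hazard ratio of 0.70, and 38 events and 54% at 0.80. The paragraph directly below the table reports that enrolment closed on 14 February 2023 and ends "The final sample size is 30".

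Protocol Section 12.3.1 had set the PFS analysis for when "36 patients have radiographically-determined disease progression or have died". SAP Section 2.1 replaces that with a single analysis: "The final planned analysis will be conducted when approximately 70% of patients have died (i.e., 21 deaths"). SAP Section 10 lists both the reduced enrolment and the merging of the two analyses as changes from the protocol. SAP Section 8.2.2 analyses PFS by Kaplan-Meier quartiles with Brookmeyer-Crowley 95% confidence intervals, plus landmark estimates at 12, 18 and 24 months.

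**The concern.** The SAP looks half updated. The death count that triggers the overall survival analysis was rescaled from 32 to 21 for the smaller trial, but the PFS figures were not. Both event counts in Table 2 exceed the number of patients, and the column heading speaks of events expected in the study, as if they still applied. Nowhere does the SAP give an event count, power or precision for 30 patients, and Section 10 reports the smaller size without its effect on the primary endpoint.

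If a reader took 80% as the power of the trial as run, an unimpressive PFS result would count as stronger evidence against a benefit than it is. At a hazard ratio of 0.70 the chance of missing the effect would be about one in three (100% − 67%), not one in five.

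**Working it through.** **Inputs.** All are from SAP Section 1.3: two-sided alpha 0.2, so z = 1.2816; control median 5.6 months; hazard ratios 0.70 and 0.80, hence medians 8.0 and 7.0 months; exponential survival; 10 months of accrual (taken as uniform) and 14 months of follow-up after the last patient is dosed.

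**Formula.** Let λ1 = ln 2 / median under the alternative. Let G(t) be the probability of still being under observation at t: 1 up to month 14, then falling linearly to 0 at month 24.

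- p1 = probability of an event = 1 − [exp(−14λ1) − exp(−24λ1)] / (10λ1)
- p0 = p1 / HR (expected events per patient under the control hazard)
- m = ∫ G(t) exp(−λ1t) λ1²t dt; then p00 = m / HR² and p01 = m / HR
- σ² = p1 − p1² + 2p00 − p0² − 2p01 + 2p0p1
- power = Φ{[√n (p0 − p1) − z√p0] / σ}

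| HR | λ1 | p1 | p0 | m | σ |
|---|---|---|---|---|---|
| 0.70 | 0.0866 | 0.8011 | 1.1445 | 0.4860 | 1.1307 |
| 0.80 | 0.0990 | 0.8413 | 1.0517 | 0.5555 | 1.0697 |

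**Reproducing Table 2 (n = 45, √n = 6.708).**

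- HR 0.70: events 45 × 0.8011 = 36.05. Power Φ[(2.303 − 1.371) / 1.1307] = Φ(0.824) = 79.5%.
- HR 0.80: events 45 × 0.8413 = 37.86. Power Φ[(1.411 − 1.314) / 1.0697] = Φ(0.090) = 53.6%.

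These match the stated 36 events / 80% and 38 events / 54%.

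**Same design with n = 30 (√n = 5.477).**

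- HR 0.70: events 24.0. Power Φ[(1.881 − 1.371) / 1.1307] = Φ(0.451) = 67.4%.
- HR 0.80: events 25.2. Power Φ[(1.152 − 1.314) / 1.0697] = Φ(−0.152) = 44.0%.

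**Ceiling with an event in all 30 patients.** Here p1 = m = 1 and σ = 1/HR.

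- HR 0.70: Φ[(2.347 − 1.532) / 1.4286] = Φ(0.571) = 71.6%.
- HR 0.80: Φ[(1.369 − 1.433) / 1.25] = Φ(−0.051) = 48.0%.

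**Sensitivity.** Actual accrual and follow-up are not in the documents, so these rest on assumptions.

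- At 21 deaths, assuming 10 to 16 months of accrual and median overall survival of 12.1 to 17.3 months: 25.0–27.7 events and 68–71% power at HR 0.70; 26.1–28.4 events and 45–47% at HR 0.80.
- With 14 months of accrual and only 6 months of minimum follow-up: 19.7 events and 62%; 21.0 events and 40%.
- A variance that averages observed and expected events would raise the ceiling to 74.4% and 50.3%. But at n = 45 it gives 82.1% and 56.1%, so it does not match Table 2 as well.
- With 30 patients, 80% power needs a hazard ratio of about 0.64 on the original schedule, or about 0.66 with complete events.

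**Where these numbers are used.** The 36-event count no longer times anything: SAP Section 2.1 uses 70% × 30 = 21 deaths. SAP Section 10 describes the dropped PFS analysis as due at about 80% of patients (36/45 = 80%). For 30 patients that share is 24, which a trial of 30 can reach. Neither Protocol Section 12.4.6.1 nor SAP Section 8.2.2 specifies a one-sample log-rank test, a p-value or a formal comparison with 5.6 months, so power does not enter any planned analysis.

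**The case for a change.** The best case for a change is that PFS remains the primary endpoint and that Section 1.3 says the size was chosen to support it. Having revised the death trigger, the authors could have carried the revision through to PFS in one sentence at no cost. No length of follow-up restores 80% power at a hazard ratio of 0.70, so the loss is real and permanent. It can also be said that the absence of a planned test makes matters worse, since the only power figures in the SAP then fit neither the sample size nor the analysis.

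The omission stands, and so does the size of the loss. What does not stand is that a stated figure is wrong or that an analysis would go astray. Table 2 is introduced as the 45-patient calculation, and the closure at 30 follows immediately beneath it. With no test planned, there is no non-significant result to set against 80%. Any replacement figure for 30 patients would also depend on accrual and follow-up that the documents do not give. The absence of a formal test is a separate question, and restating power would not settle it.

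**Conclusion.** No change follows. Table 2 is a correct record of the original design and is identified as such by its introductory text; the reduction to 30 and the merged analysis are both disclosed. For 30 patients on the original accrual and follow-up, the design would have expected about 24 to 25 PFS events, with power of about 67% at a hazard ratio of 0.70 and 44% at 0.80, and at most about 72% and 48%. These figures assume exponential survival, uniform accrual and the one-sample log-rank test; shorter follow-up would lower them.

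Enrolment was already closed, so the sample size could no longer respond to a power figure. An analyst following the SAP as written will produce the same Kaplan-Meier estimate and the same 95% confidence interval whether or not Section 1.3 restates power, and that interval shows directly how much 30 patients can say. A reader who wants the power for 30 can obtain it from the inputs that Section 1.3 gives.

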2. THE NUMBER OF PLANNED ANALYSES

2.1. Final Planned Analysis - Analyses for Progression Free Survival, Tumor Response Endpoints, Myelosuppression Endpoints, and Overall Survival

The final planned analysis will be conducted when approximately 70% of patients have died (i.e., 21 deaths). Study database will be locked to support the final OS analysis. The following specified analyses will be performed:

- Analysis of progression free survival.
- Analysis of tumor response endpoints (ORR, CBR, and DOR).
- Analysis of myelosuppression endpoints.
- Analysis of overall survival.
- Analysis of safety data.

The final planned analysis will be used to support the abbreviated clinical study report (aCSR).

G1 Therapeutics

3. ANALYSIS POPULATIONS

3.1. The Full Analysis Set

The full analysis set (FAS) includes all enrolled patients who received at least one dose of study drug. Unless otherwise specified, the FAS is the primary analysis set for all efficacy analyses.

3.2. The Response Evaluable Population

The Response Evaluable (RE) population includes all patients who are in the FAS, have measurable (target) tumor lesion(s) at baseline tumor assessment per RECIST v1.1, and have either of the following:

- 1. At least one post-baseline tumor assessment.
- 2. Discontinued treatment because of clinical progression prior to the first post-baseline tumor scan.
- 3. Died due to disease progression prior to the first post-baseline tumor scan.

The RE population will be the primary population for efficacy endpoints evaluating tumor responses.

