In 2020, accelerated approval was granted by FDA for sacituzumab govitecan-hziy (Trodelvy®) for the treatment of adult patients with metastatic TNBC who have received at least two prior therapies for metastatic disease. Sacituzumab govitecan-hziy is a trophoblast cell surface antigen 2 (Trop-2)-directed antibody-drug conjugate linked to SN-38, the active metabolite of irinotecan, a topoisomerase I inhibitor (for more information, refer to Section 6.5). The accelerated approval was based on results from the Phase 2 IMMU-132-01 trial where patients (N=108) treated with sacituzumab govitecan-hziy had an objective response rate (ORR) of 33.3%, median duration of response (DOR) of 7.7 months (95% CI: 4.9-10.8 months), and 55.5% and 16.7% of patients having a DOR of ≥6 months and ≥12 months, respectively (Bardia, 2019). In 2021, full approval was granted by FDA based on the results from the Phase 3 ASCENT trial (Bardia, 2021). Median PFS for patients receiving sacituzumab govitecan-hziy was 4.8 months (95% CI: 4.1-5.8 months) compared with 1.7 months (95% CI:1.5-2.5 months) in those receiving physician's choice of single-agent chemotherapy (hazard ration [HR] 0.43, 95% CI: 0.35-0.54, P<0.0001) and median overall survival (OS) was 11.8 months (95% CI: 10.5-13.8 months) and

G1T28-213

6.9 months (95% CI: 5.9-7.6 months), respectively (HR 0.51, 95% CI: 0.41-0.62, P< 0.0001) (Trodelvy Package Insert, 2021). In that same study, in a subset of patients without brain metastasis at baseline (88% of the full study population), median PFS for patients receiving sacituzumab govitecan-hziy was 5.6 months (95% CI: 4.3-6.3 months) compared with 1.7 months (95% CI: 1.5-2.5 months) in those receiving physician's choice of single-agent chemotherapy (HR 0.41, 95% CI: 0.32-0.52, P<0.001) and median OS was 12.1 months (95% CI: 10.7-14.0 months) and 6.7 months (5.8-7.7 months), respectively (HR 0.48, 95% CI: 0.38-0.59, P<0.001) (Bardia, 2021).

[figure not shown]

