# 12.2. Analysis Population

The following analysis populations are defined for the study.

The full analysis set (FAS) includes all enrolled patients who were administered at least 1 dose of study drug. Unless otherwise specified, the FAS is the primary analysis set for all efficacy analyses.

The response evaluable (RE) population includes all patients who are in the FAS and who have measurable (target) tumor lesion(s) at the baseline tumor assessment and either (i) have at least 1 post-baseline tumor assessment, or (ii) do not have post-dose tumor assessment but have clinical progression as noted by the Investigator, or (iii) died due to disease progression prior to their first post-baseline tumor scan. The RE population will be the primary analysis set for tumor response analyses.

The safety population includes all enrolled patients who received at least 1 dose of study drug. All safety analyses will be evaluated using the safety population.

G1T28-213

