8.2.3. Analysis for Secondary Endpoints - Anti-tumor Efficacy Endpoints

The analysis for BOR, CBR, and ORR (see variable definitions in Section 8.1.2) will be based on the RE population.

Tumor response status classified by BOR will be tabulated with the number and percentage of patients in each category of CR, PR, SD, PD or NE, where the percentages are calculated based on the number of patients in the RE population.

ORR along with its exact 95% two-sided CI using the Clopper-Pearson method will be computed.

Confirmed ORR and CBR will be summarized and analyzed using the same methods as are used for the ORR.

For patients who achieved CR or PR as BOR status, DOR will be analyzed. The Kaplan-Meier method will be used to estimate the median, 25% and 75% percentile of DOR, along with its 95% CI calculated using the method by Brookmeyer and Crowley (1982).

Data listings will include tumor scan data, Investigator determined timepoint responses and BOR, and programmatically derived tumor response status, and confirmed tumor response status.

G1 Therapeutics

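### Some treated patients with no post-baseline scan are left out of the ORR and CBR denominators, so these rates can err only upward, and no all-treated result is planned beside them

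*SAP*

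**What the plan says.** SAP 3.1 makes the all-treated set the default for efficacy: "The full analysis set (FAS) includes all enrolled patients who received at least one dose of study drug". Tumor response is the exception. Protocol 12.2 states: "The RE population will be the primary analysis set for tumor response analyses". SAP 8.2.3 repeats this: "The analysis for BOR, CBR, and ORR (see variable definitions in Section 8.1.2) will be based on the RE population". Confirmed ORR is handled by the same methods.

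SAP 3.2 admits an FAS patient with measurable disease at baseline to the RE population if one of three conditions holds:

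- "At least one post-baseline tumor assessment"
- "Discontinued treatment because of clinical progression prior to the first post-baseline tumor scan"
- "Died due to disease progression prior to the first post-baseline tumor scan"

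Protocol 12.2 words the second condition more widely. It covers patients who "do not have post-dose tumor assessment but have clinical progression as noted by the Investigator" and does not require that treatment was stopped for that reason.

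SAP 8.1.2, 8.2.1 and 8.2.3 contain no response analysis on the FAS, and SAP 8.3 rules out imputation of missing data.

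**The concern.** Whether an unscanned patient counts depends on why there was no scan. Early clinical progression or death from disease keeps the patient in as a non-responder. Death from toxicity or another cause, withdrawal or loss to follow-up takes the patient out, as does stopping for an adverse event with no later scan. From the standpoint of what the regimen achieved in treated patients, all of these are failures to respond.

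The rule also treats the same patient differently across endpoints. A patient who dies of toxicity before the first scan is a PFS event on the FAS under SAP Table 6, but disappears from ORR and CBR. One report would then count that failure in the primary endpoint and omit it from the secondary ones.

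At stake is how the response rates of a small single-arm study are read. Nothing in the plan shows how far the RE rate lies from the all-treated rate.

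**Working it through.** **No stated figure to reproduce.** The documents give no sample size, power, precision target or threshold for ORR or CBR. The only powered calculation (Protocol 12.1, SAP 1.3) concerns PFS, which is analyzed on the FAS and is not affected.

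**Inputs**

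- Enrolled patients: 30 (SAP 1.1). I assume all were dosed, so N_FAS = 30.
- Measurable disease is an entry criterion (Protocol 7.1). I assume every patient met it, so the only way out of RE is to have no post-baseline scan and no qualifying progression or death.
- First scheduled scan: week 6, ±7 days (Protocol 11.2.1).
- k, the number of FAS patients outside RE: not in the documents. Shown for 0 to 6.
- Responders: 10, purely as an illustration. Patients with clinical benefit: 15, likewise.

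**Step 1: who leaves.** I checked each reason for having no post-baseline scan against SAP 3.2:

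| Patient with no post-baseline scan who | In RE? |
|---|---|
| stopped treatment for clinical progression | yes |
| died of disease progression | yes |
| died of toxicity or another cause | no |
| withdrew or was lost to follow-up | no |
| stopped for an adverse event and was never scanned | no |
| had clinical progression noted, but stopped for another recorded reason | no under SAP 3.2; yes under Protocol 12.2 |

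**Step 2: direction.** Without a post-baseline scan a patient cannot be a CR, a PR or a stable disease lasting 24 weeks. The numerator r is therefore the same in both sets:

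rate_FAS = r / N_FAS

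rate_RE = r / (N_FAS − k) = rate_FAS × N_FAS / (N_FAS − k)

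The multiplier is 1 at k = 0 and above 1 for every k ≥ 1.

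**Step 3: size.** With N_FAS = 30:

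| k | Multiplier 30/(30 − k) | ORR, 10 responders | Excess over FAS (points) |
|---|---|---|---|
| 0 | 1.000 | 10/30 = 33.3% | 0.0 |
| 1 | 1.034 | 10/29 = 34.5% | 1.1 |
| 2 | 1.071 | 10/28 = 35.7% | 2.4 |
| 3 | 1.111 | 10/27 = 37.0% | 3.7 |
| 4 | 1.154 | 10/26 = 38.5% | 5.1 |
| 6 | 1.250 | 10/24 = 41.7% | 8.3 |

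The Clopper-Pearson 95% intervals are 17.3% to 52.8% for 10/30 and 20.2% to 59.4% for 10/26.

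For CBR with 15 patients benefiting, 15/30 = 50.0% becomes 15/28 = 53.6% at k = 2 and 15/26 = 57.7% at k = 4.

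**Step 4: is the gap visible elsewhere?** SAP 8.1.2 has a Not Evaluable category for best overall response, but SAP 8.2.3 computes its percentages on RE, so it cannot hold patients already excluded. The disposition summary in SAP 5.1 gives reasons for stopping drug and study, but does not tabulate exclusions from RE.

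**The case against.** The case on the other side is substantial.

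- **The exclusions may be few or none.** The number is not given. Entry requires ECOG 0 or 1 and a predicted life expectancy of at least 3 months (Protocol 7.1), which argues against many losses before week 6. A reader might infer that the reported rates will in fact be inflated, or that three or four exclusions are expected. Neither is supported: only the direction is established, and at k = 0 the two sets agree.
- **Stopping drug does not stop scanning.** A reader might infer that every patient who stops early for an adverse event is dropped. Protocol 10.1 and 11.2.1 ask that scans continue after discontinuation without progression, and one later scan puts the patient in RE. What remains is the patient who is never scanned again. That can happen, because scanning is on a best-effort basis and ends when new anticancer therapy begins.
- **No ORR benchmark is tested.** Protocol 4.1 cites an earlier trial "where patients (N=108) treated with sacituzumab govitecan-hziy had an objective response rate (ORR) of 33.3" percent, which is 36/108. A reader might infer that the plan makes an invalid comparison with this figure. It does not. The historical control is used for PFS only, and the ORR figure is background. Its denominator looks like all treated patients, but that trial's evaluability rule is not in the documents.
- **The definition is pre-specified and is not scanned-only.** It retains early clinical progressors and disease deaths. A reader given both denominators can divide RE responders by the FAS count.
- **The interval is wide.** A shift of 5.1 points at k = 4 is small beside an interval of about 35 points (52.8 − 17.3 = 35.5).

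These points limit the importance of the matter; they do not remove it. Imprecision does not offset an error that can go only one way. Readers should not have to rebuild the all-treated rate and its interval themselves.

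**Conclusion.** The point holds as a cheap improvement. For ORR, confirmed ORR and CBR, the RE rate can equal or exceed the FAS rate and cannot fall below it, and the plan has no FAS result to set beside it. The size is unknown because k is unknown. On the illustration of 10 responders among 30 dosed patients, the excess runs from 0 at k = 0 to 5.1 points at k = 4.

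This rests on all 30 enrolled patients having been dosed and having had measurable disease at baseline. The count of 10 responders is not a prediction.

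The consequence is confined to descriptive secondary endpoints and how they are interpreted. No decision rule depends on them, and PFS, OS and DOR are unaffected.

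Separately, SAP 3.2 narrows the protocol's clinical-progression criterion by requiring that treatment was stopped for that reason. This can remove further non-responders. The SAP states that it takes precedence over the protocol, and SAP Section 10 does not list the change.

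**What to change.** 1. In SAP 8.2.3, add ORR, confirmed ORR and CBR on the FAS, counting patients with no post-baseline assessment as non-responders, with the same Clopper-Pearson intervals. Show them beside the RE results.
2. Report the number of FAS patients excluded from RE, with the reason for each.
3. Reconcile the clinical-progression criterion in SAP 3.2 with Protocol 12.2, or list the change in SAP Section 10.

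The cost is one extra table column, a short exclusion summary and one edit to the SAP text. No new data are needed. The downside is that the added rate may be lower than the RE rate. If nobody is excluded, the two columns agree and the question is closed.
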